## 5. Study Design

### 5.1. Overall Design

Study J1E-MC-JZEA (JZEA) is a multicenter, nonrandomized, open-label, first in human Phase 1 study in patients with advanced solid tumors.

Phase 1 study will assess the safety and tolerability of LY3434172, administered as a monotherapy in patients with select advanced solid tumors (see [Figure JZEA.1](#)). LY3434172 will be administered as an IV bolus injection for doses less than 100 mg (approximately 5 to 10 minutes) and for doses  $\geq$ 100 mg, IV infusion over approximately 60 minutes. Patients enrolled into Cohorts A1 through A5/6 will be administered LY3434172 on a Q2W dose schedule. Cohort A6 is an optional cohort that may be explored at a dose not exceeding 1000 mg of LY3434172 based on safety, PK, and pharmacodynamic data. Dose escalation will be driven by modified toxicity probability interval 2 (mTPI2) method (Guo et al. 2017), enrolling at least three patients per cohort. Further discussion on dose escalation is explained in Section [5.1.1](#).

To facilitate a thorough safety evaluation and exploration of PK and pharmacodynamics effects of the every two week (Q2W) dosing schedule (Cohorts A1 to A6) will be explored. Once dose-limiting toxicity (DLT) period is completed for respective Cohorts A1 to A5/6 up to approximately 12 to 15 additional patients may be added to two dose levels selected from these cohorts (see [Figure JZEA.1](#)). After evaluating PK/pharmacodynamic data from these cohorts, any doses from the dose escalation range could be used in order to cover the entire predicted biologically effective dose (BED) and allow for uncertainty around it (see Section 5.5). For example, if 300 mg is a dose level selected, additional patients may be enrolled in parallel with Cohort A5 after Cohort A4 has cleared DLT.

In addition, an every three-week (Q3W) dosing schedule (Cohorts A7 and A8) will be evaluated to allow for flexibility for future combinations with standard-of-care agents that may use a Q3W dose regimen. The Q3W dosing schedule could be initiated as Cohorts A7 and A8 in parallel with the enrollment of additional patients enrolled into two dose levels of the Q2W schedule, respectively.

Ongoing safety reviews between the Lilly and the investigators will be conducted after completion of the DLT period for each cohort to ensure it is safe to continue with the next dose-escalation cohort.

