### 5.1.1. Dose Escalation

The first patient will be enrolled in Cohort A1 and treated according to a Q2W dosing regimen (see [Figure JZEA.1](#)). CCI

A DLT

observation period of 28 days (42 days in Cohort A1) will apply to all patients on the Q2W dosing regimen in subsequent cohorts. Ongoing safety reviews between the Lilly clinical research physician/clinical research scientist (CRP/CRS) and the investigators will be conducted during and upon completion of the DLT period for each cohort, to ensure it is safe to continue with the next dose-escalation cohort.

After the first patient in Cohort A1 receives the first dose of LY3434172, there will be a delay of 1 week before the second patient receives LY3434172 to allow for safety observation. In all subsequent cohorts, the first patient in each dose level will be observed for approximately 24 hours before any additional patients are treated; no additional delays are required for subsequent patients in the same cohort.

Patients in Cohorts A2, A3, A4, A5, and A6 (optional), respectively, CCI provided safety is established in the preceding cohorts. Once DLT period of 28 days for Q2W, except Cohort A1 with 42 day DLT, is completed for respective dose levels within Cohorts A1 to A5/A6, two dose

levels, yet to be determined but will be selected from these cohorts, can be expanded between 12 and 15 patients in total. Pharmacokinetic, pharmacodynamic and safety data evaluated during the course of the dose escalation will be used to select these two dose levels. The purpose of expanding to additional 12-15 patients is to further inform safety, PK and pharmacodynamics. These cohorts will continue to enroll while interim analysis (IA) is ongoing.

Cohorts of patients will be treated with escalating doses of LY3434172 according to an mTPI-2 method until the criteria for reaching the maximum-tolerated dose (MTD) are met. For some immuno-oncology compounds that have manageable safety profiles and do not reach a MTD, additional information such as pharmacodynamic markers may be helpful in determining the appropriate RP2D (Agrawal et al. 2016; Parchment et al. 2016).

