### 7.2.2.2. Dose-Limiting Toxicity Determination

A DLT is defined as any of the events listed in [Table JZEA.8](#), if both the following criteria are met:

- the event occurs during the DLT observation period (Cycle 1, 42 days) for Cohort A1, (Cycle 1, 28 days) for Cohorts A2 to A5 (A2 to A6 if Cohort A6 is opened), (Cycle 1 and 2, 42 days) for Cohorts A7 and A8, and
- the event is clinically significant and definitely, probably, or possibly related to LY3434172, in the opinion of the investigator.

Patients in Cohorts A1 to A5/6, A7, and A8 who experience a DLT in Cycle 1 will be discontinued from study treatment.

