#### **7.2.2.2 DLT-Equivalent Toxicities**

A DLT-equivalent toxicity (ET) is an AE that meets the DLT criteria as defined above and occurs in any cycle other than the DLT assessment period (28 days for Q2W schedule and 42 days for Q3W schedule). In addition to the DLT assessment period, available safety data beyond the DLT assessment period may also be taken into consideration prior to a decision to advance to the next dose level or the determination of the RP2D.

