#### 10.3.1. Safety Analyses

All patients who receive any quantity of LY3434172 will be evaluated for safety and toxicity. Severity grades will be assigned by the investigator using CTCAE Version 5.0.

Safety analyses will include summaries of the following:

- DLTs: the number of patients who experience any DLTs during Cycle 1 will be summarized by cohort by treatment arm
- DLT-equivalent: the number of patients who experience any AE that qualifies as a DLT during any period of study will be summarized by the first dose by treatment arm and by tumor type
- AEs, including severity and possible relationship to study drug
- AEs by Medical Dictionary for Regulatory Activities system organ class (SOC) by decreasing frequency of Preferred Term within an SOC
- laboratory and non-laboratory AEs by CTCAE Version 5.0 term, maximum CTCAE grade, and CTCAE Grade 3 and above (regardless of causality and at least possibly related to study treatment)
- changes in vital signs and ECGs

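### DLT-equivalent toxicity, a primary safety endpoint, has conflicting counting rules, and the windows that separate it from DLTs do not match for Cohorts A1, A7 and A8

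*Protocol*

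**What the plan says.** DLT-equivalent toxicities are listed among the endpoints for the primary objective (Protocol Section 4, Table JZEA.6).

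- **Definition.** Under Protocol 7.2.2.2.2 (DLT-Equivalent Toxicities), the event meets the DLT criteria and "occurs in any cycle other than the DLT assessment period (28 days for Q2W schedule and 42 days for Q3W schedule").
- **Summary.** Protocol 10.3.1 tabulates "the number of patients who experience any AE that qualifies as a DLT during any period of study", with no exclusion. The DLT summary just above it covers "the number of patients who experience any DLTs during Cycle 1 will be summarized by cohort by treatment arm".
- **Windows.** Protocol 7.2.2.2 sets "the DLT observation period (Cycle 1, 42 days) for Cohort A1", 28 days for A2 to A5/A6, and "Cycle 1 and 2, 42 days) for Cohorts A7 and A8". Protocol 5.1.1 agrees on A1: "observation period of 28 days (42 days in Cohort A1").
- **Schedule.** "Patients enrolled into Cohorts A1 through A5/6 will be administered LY3434172 on a Q2W dose schedule" (Protocol 5.1), so A1 is a Q2W cohort. Protocol 7.2.1 sets the cycle at 28 days for Q2W and 21 days for Q3W.
- **SAP.** Section 6.12.2 takes both definitions from Protocol 7.2.2.2. It reports DLTs on the DLT-evaluable population and DLT-equivalents on the safety population. Section 6.2.1 equates the DLT observation period with Cycle 1 when it defines the DLT-evaluable population.

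**The concern.** A DLT-equivalent count is useful because it isolates toxicity of DLT grade that the DLT window did not capture. Protocol 7.2.2.2.2 itself says that safety data from beyond that window may be considered when advancing dose or choosing the RP2D. A count that also takes in the DLTs measures something else.

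The protocol and the SAP can lead two programmers to different tables for the same endpoint. Protocol 10.3 says that changes to its analysis methods will be described and justified in the SAP and the clinical study report, and the SAP declares no departure from 10.3.1. The reader therefore cannot tell whether SAP 6.12.2 was meant to replace the 10.3.1 rule or to restate it.

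The time windows also fail to split follow-up cleanly. Some days count as both kinds of event, and some days inside a DLT window are missing from the DLT summary.

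**Working it through.** The plan gives no figure to reproduce. The check classifies study days by cohort under each rule. The DLT window comes from Protocol 7.2.2.2, the excluded days from Protocol 7.2.2.2.2, and the cycle length from Protocol 7.2.1.

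| Cohorts | DLT window | Days excluded by the DLT-equivalent definition | Cycle 1 | In window and counted by the 10.3.1 DLT-equivalent summary | In window and also meeting the definition | In window but after Cycle 1 |
|---|---|---|---|---|---|---|
| A1 | 1-42 | 1-28 | 1-28 | 1-42 | 29-42 (42 - 28 = 14 days) | 29-42 (14 days) |
| A2-A6 | 1-28 | 1-28 | 1-28 | 1-28 | none | none |
| A7-A8 | 1-42 | 1-42 | 1-21 | 1-42 | none | 22-42 (42 - 21 = 21 days) |

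**Step 1: the 10.3.1 summary against the definition.** Let D be the patients with a DLT in the window, L those with a qualifying event after it, and B those with both. The literal 10.3.1 count is D + L - B, and the definition gives L. The difference is D - B, the patients whose only qualifying events were DLTs. Subtracting the DLT row does not recover L in general: (D + L - B) - D = L - B. The rows are not directly comparable either. Under the SAP they use different populations. In 10.3.1 DLTs are split by cohort and arm, and DLT-equivalents by first dose, arm and tumor type.

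**Step 2: Cohort A1.** The definition's 28 days for Q2W has no exception for A1. An A1 event on days 29-42 is a DLT under 7.2.2.2 and a DLT-equivalent under 7.2.2.2.2. The SAP imports both definitions, so following the SAP does not remove this overlap.

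**Step 3: Cycle 1.** An A7-A8 DLT on days 22-42 is in Cycle 2, so the 10.3.1 DLT summary omits it. The any-period DLT-equivalent summary would still pick it up. A1 days 29-42 are ambiguous: Protocol 7.2.2.2 labels the 42-day window as Cycle 1, but Protocol 7.2.1 makes a Q2W cycle 28 days.

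**Step 4: the repair.** If only the DLT-equivalent summary were limited to time outside the window, A7-A8 days 22-42 would fall in neither row of 10.3.1. If both rows use the same cohort-specific window, no day falls in both rows and no day falls in neither, in any cohort.

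**The case against.** A reader might infer that every DLT patient will be counted twice. The documents do not establish that. The 10.3.1 item carries a defined term as its label and can be read subject to the definition, and a table built from SAP 6.12.2 would apply the exclusion. The double count follows only from 10.3.1 taken literally. What remains is that the documents do not say which rule governs.

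A reader might also infer that late toxicity would be hidden. It would not. SAP 6.12.2 lists DLT-equivalents, and SAP 6.12.3 lists all adverse events by patient with start and end dates, so late events can be identified under any reading. The summary row is less informative, but nothing is lost from the record.

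A third inference is that dose decisions are affected. Escalation uses DLT counts in the Appendix 8 table, the RP2D rests on the totality of data (Protocol 7.2.2.3), and no dose rule uses the 10.3.1 DLT-equivalent count.

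The A1 mismatch may be an abbreviated parenthesis that forgot one cohort with a minimum of three patients. That limits its size. It remains a contradiction in the definition that both documents rely on.

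**Conclusion.** The concern holds as an inconsistency in how a primary safety endpoint is defined and reported. It has three parts:

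- Two rules for DLT-equivalents, differing by D - B patients if 10.3.1 is taken literally.
- A 14-day overlap in Cohort A1 under the definitions themselves.
- A 21-day stretch in Cohorts A7-A8 that is inside the DLT window but outside the 10.3.1 DLT summary.

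The day counts follow directly from the documents. The A7-A8 result assumes that Cycle 1 means 21 days for Q3W, as Protocol 7.2.1 states. No percentage can be put on the first part, because it depends on event counts that nobody yet has. The mTPI-2 rules in Appendix 8 are unaffected, and the individual events can be recovered from the listings. This should be corrected before the tables are programmed.

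**What to change.** **Protocol 10.3.1.** Summarize DLTs *during the patient's DLT observation period* in place of the Cycle 1 limit. Summarize DLT-equivalents *outside the patient's DLT observation period* in place of the any-period wording. Make both edits together, since changing the second alone opens the A7-A8 gap in Step 4. If a cumulative count is wanted, give it its own labelled row.

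**SAP 6.2.1.** Replace the Cycle 1 reference in the DLT-evaluable population with the same term.

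**Windows.** Reconcile Protocol 5.1.1, 7.2.1, 7.2.2.2, 7.2.2.2.2 and 8.1 so that each cohort has one stated DLT window, used for both definitions. Section 8.1 makes a DLT in Cycle 1 and a DLT-equivalent toxicity reasons to stop study treatment, so these windows also bear on patient management. The sponsor must decide how to reconcile them; this review does not propose which window is right.

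**Cost.** Two wording edits in 10.3.1, one SAP alignment and the reconciliation of the window statements. The reporting edits need no new data and leave the Appendix 8 table as it is. The window reconciliation needs a clinical decision because of Section 8.1.

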### **10.3.2. *Efficacy Analyses***

The study was not designed to make an efficacy assessment. However, any tumor response data will be tabulated, where appropriate, for all patients in the enrolled/safety analysis set.

The efficacy endpoints are listed and defined as follows:

**Objective response rate (ORR)** is the proportion of enrolled patients who have received any amount of either study drug, have at least one postbaseline tumor image, and achieved a best overall response (BOR) of confirmed CR or PR.

**Duration of response (DoR)** is defined only for responders (patients with a confirmed CR or PR). It is measured from the date of first evidence of a confirmed CR or PR to the date of the first observed radiographically documented PD, or the date of death due to any cause, whichever is earlier. If a responder is not known to have died or have objective progression as of the data inclusion cutoff date, DoR will be censored at the date of the last complete objective progression-free disease assessment.

**Time-to-response (TTR)** is the time from the date of first study treatment until the first evidence of a confirmed CR or PR.

**Disease control rate (DCR)** is the proportion of enrolled patients who have a BOR of confirmed CR, confirmed PR, or stable disease (SD).

**Progression-free survival** is defined as the time from the date of first study treatment until the date of the first observed radiographically documented PD or death due to any cause, whichever is earlier. The censoring is taken in the following order:

- If a patient does not have a complete baseline disease assessment, then the PFS time will be censored at the enrollment date, regardless of whether or not objectively determined disease progression or death has been observed for the patient; otherwise,

- if a patient is not known to have died or have objective progression as of the data inclusion cutoff date for the analysis, the PFS time will be censored at the last complete objective progression-free disease assessment date.

**Overall survival**, an exploratory objective, is determined from the date of first study treatment until death due to any cause. If the patient is not known to have died at the data inclusion cutoff date for the analysis (or is lost to follow-up), OS will be censored on the last date the patient was known to be alive. This endpoint will be followed up for 12 months after the last patient has entered treatment.

The objective response rate, TTR, DCR, DoR, and PFS will be assessed based on RECIST v1.1 (Eisenhauer et al. 2009) and RECIST v1.1 with confirmatory scan for disease progression (Section 9.1.1).

The estimate of ORR and DCR, and the corresponding CI, will be provided by dose-level (cohort) according to RECIST v1.1 and RECIST v1.1 with confirmatory scan for disease progression (Section 9.1.1). Time-to-event variables, such as TTR, DoR, PFS (as an exploratory objective), and OS (as an exploratory objective), will be summarized by Kaplan and Meier (1958) method by dose-level (cohort) where appropriate. Presentations of antitumor activity may include patients enrolled in the dose-level (cohort) with the same tumor type and dosing scheme. Individual changes in the tumor burden over time will be presented graphically within a tumor type. Subgroup analysis of interest will be further defined in the SAP.

### **10.3.3. Other Analyses**

#### **10.3.3.1. Patient Disposition**

A detailed description of patient disposition will be provided, including a summary of the number and percentage of patients entered into the study, enrolled in the study, and treated as well as number and percentage of patients completing the study, as defined in the SAP, or discontinuing (overall and by reason for discontinuation). A summary of all important protocol deviations will be provided.

#### **10.3.3.2. Patient Characteristics**

Demographic data are collected and reported using descriptive statistics.

A summary of baseline patient and disease characteristics, historical diagnoses, preexisting conditions, and prior therapies will be reported using descriptive statistics.

Other patient characteristics at baseline will be summarized as deemed appropriate.

#### **10.3.3.3. Concomitant Therapy**

A summary of prior and concomitant medications will be reported.

#### **10.3.3.4. Treatment Compliance**

The number of cycles received, dose omissions, dose reductions (if any), dose delays, and dose intensity will be summarized for all treated patients by treatment arm.

LY3434172 will be administered at the investigator site, therefore treatment compliance is assured.

#### **10.3.3.5. Pharmacokinetic/Pharmacodynamic Analyses**

Selected PK descriptors (based on actual sampling times), including approximate  $C_{max}$  and AUC will be calculated by noncompartmental analysis methods. As an exploratory analysis, PK descriptor estimates for trough concentrations ( $C_{min}$ ) at steady state following repeated dose may be evaluated.

In addition, PK parameter estimates for LY3434172 may be calculated by population PK analysis methods using nonlinear mixed effects modeling (NONMEM). The version of any software used for the analysis will be documented, and the program will meet the Lilly requirements of software validation. It is possible that other validated, equivalent PK software programs may be used if appropriate, warranted, and approved by Global PK/pharmacodynamic management.

Following review of the biomarker analyses (see Section 10.3.3.6), pharmacodynamics biomarker analysis with tumor type, changes in biomarker levels over time, and association to dose levels or exposure might be explored if applicable. Pharmacokinetics/Pharmacodynamics analyses may be conducted to explore exposure-response relationships between LY3434172 concentrations in systemic circulation and relevant pharmacodynamics measures such as soluble PD-1, soluble PD-L1 and IL-2 stimulation. Either summary metrics of exposure and effect (for example, individual trough concentrations) or concentration time profiles of exposure and effect could be used for these analyses.

#### **10.3.3.6. Biomarker Analyses**

The relationship between biomarkers and clinical outcome may be assessed. If the ORR is greater than or equal to 10%, the baseline biomarkers that potentially predict better response to LY3434172 may be explored using single- or multi-marker approach. Association analysis from selected biomarkers to the clinical endpoints will be explored if applicable.

#### **10.3.3.7. Immunogenicity Analyses**

The frequency and percentage of patients with preexisting ADA, ADA at any time point postbaseline, and with treatment-emergent ADA positivity (TE ADA+) to LY3434172 will be tabulated. Treatment-emergent ADAs are defined as those with a titer 2-fold (1 dilution) greater than the minimum required dilution if no ADAs were detected at baseline (treatment-induced ADA) or those with a 4-fold (2 dilutions) increase in titer compared to baseline if ADAs were detected at baseline (treatment-boosted ADA). For the TE ADA+ patients, the distribution of maximum titers will be described. The frequency of neutralizing antibodies may also be tabulated in TE ADA+ patients.

The relationship between the presence of antibodies and the PK parameters and pharmacodynamic response including safety and efficacy to LY3434172 may be assessed.

#### ***10.3.4. Interim Analyses***

Safety, PK, and biomarker data (if available) will be reviewed on a cohort-by-cohort basis during the study, until the MTD and/or RP2D is determined. The purpose of these cohort-by-cohort data reviews is to evaluate the safety data at each dose level and determine if a DLT has been observed. The decision whether to advance to the next dose level will be made following discussion between the investigators and Lilly and will be relayed to the sites prior to patients being treated on the subsequent cohort.

Safety and available PK data will be reviewed during the study to inform dose escalation, modifications to the dose-escalation strategy, or other design elements.

An interim analyses will be performed after all patients from cohorts A1 to A5/6 have completed the DLT evaluation period. Additional enrolment of 12-15 patients from these cohorts at two dose levels (yet to be determined) can continue during IA.

Interim analyses may also be combined with any prespecified safety review or reporting (i.e. Trial Level Safety Reviews, Development Safety Update Reviews, or IB update reviews).

The final overall analysis of Study JZEA will coincide with the safety and efficacy primary analysis of the last cohort.

If it is deemed that enough data have been obtained to assess the primary and secondary objectives, a CSR might be created before the last patient visit. In this case, all data until the data-cutoff date will be used for the analysis of safety, efficacy, PK, and pharmacodynamic biomarkers. All data defined in the protocol will continue to be collected from patients on treatment after data-cutoff date and results may be listed. However, summary tables including data after data-cutoff date will not be created.

## 12. Appendices

---

## Appendix 1. Abbreviations and Definitions

---

Term	Definition
ADA	anti-drug antibody
AE	Adverse event: any untoward medical occurrence in a patient or clinical investigation patient administered a pharmaceutical product and does not necessarily have a causal relationship with this treatment. An adverse event can therefore be any unfavorable and unintended sign (including an abnormal laboratory finding), symptom, or disease temporally associated with the use of medicinal (investigational) product, whether or not related to the medicinal (investigational) product.
ALT	alanine aminotransferase
ANC	absolute neutrophil count
aPTT	activated partial thromboplastin time
ASCO	American Society of Clinical Oncology
AST	aspartate aminotransferase
AUC	area under the concentration-time curve
BED	biologically effective dose
BOR	best overall response
Cavg	2-week average concentration
Cmax	maximum plasma concentration
Cmin	trough concentration
CBC	complete blood count
cDNA	complementary DNA
CI	confidence interval
CL	clearance
CNS	central nervous system
collection database	A computer database where clinical study data are entered and validated.

CR	complete response
CrCl	creatinine clearance
CRP	clinical research physician: individual responsible for the medical conduct of the study. Responsibilities of the CRP may be performed by a physician, clinical research scientist, global safety physician or other medical officer.
CRS	clinical research scientist
CSR	clinical study report
CT	computed tomography
CTCAE	Common Terminology Criteria for Adverse Events
Ctrough	lowest concentration of drug just prior to the next dose
DCR	disease control rate: the percentage of patients with a best response of CR, PR, or SD.
DLT	dose-limiting toxicity
DLT-ET	DLT-equivalent toxicity
DoR	duration of response: the time from the date measurement criteria for CR or PR (whichever is first recorded) are first met until the first date that disease is recurrent or objective progression is observed, per RECIST 1.1 criteria, or the date of death from any cause in the absence of objectively determined disease progression or recurrence.
ECG	electrocardiogram
eCRF	electronic case report form
EI	equivalence interval
enroll	The act of assigning a patient to a treatment. Patients who are enrolled in the study are those who have been assigned to a treatment and have received at least one dose of study treatment.
ERBs/IRBs	ethical review boards/institutional review boards
Enter	Patients entered in the study are those who have signed the informed consent form directly or through their legally acceptable representatives.
ESR	erythrocyte sedimentation rate
FDA	Food and Drug Administration
FIH	first in human
GCP	good clinical practice

G-CSF	granulocyte colony stimulating factors
GFR	glomerular filtration rate
HCC	hepatocellular
highly effective method of contraception	Methods include 

combined (estrogen and progestogen containing) hormonal contraception associated with inhibition of ovulation:

oral

intravaginal

transdermal

progestogen-only hormonal contraception associated with inhibition of ovulation:

oral

intravaginal

transdermal

intrauterine device

intrauterine hormone-releasing system

bilateral tubal occlusion

vasectomized partner (vasectomized partner is a highly effective birth control method provided that partner is the sole sexual partner of the woman of childbearing potential who is the trial participant and that the vasectomized partner has received medical assessment of the surgical success.)

sexual abstinence (sexual abstinence is considered a highly effective method only if defined as refraining from heterosexual intercourse during the entire period of risk associated with the study treatments. The reliability of sexual abstinence needs to be evaluated in relation to the duration of the clinical trial and the preferred and usual lifestyle of the subject.)

HIV	human immunodeficiency virus
IB	Investigator's Brochure
irAEs	immune-related adverse events
IRR	infusion-related reaction
ICF	informed consent form
ICH	International Conference on Harmonization
IG	immunogenicity
IgG	immunoglobulin G
IgG1	immunoglobulin G1
IgM	immunoglobulin M

interim analysis	An analysis of clinical study data that is conducted before the final reporting database is authorized for datalock.
IRR	infusion-related reaction
irRC	immune-related response criteria
Investigational product	A pharmaceutical form of an active substance or placebo being tested or used as a reference in a clinical study including products already on the market when used or assembled (formulated or packaged) in a way different from the authorized form, marketed products used for an unauthorized indication or marketed products used to gain further information about the authorized form.
IV	intravenous
IWRS	interactive web-response system
LPET	last patient enters/starts study treatment
mAb	monoclonal antibody
MABEL	minimum anticipated biological effect level
MPO	myoperoxidase
MTD	maximum tolerated dose
mTPI-2	modified toxicity probability interval-2
NK cells	natural killer cells
NOAEL	no-observed-adverse-effect-level
NONMEM	nonlinear mixed effects modeling
NSCLC	non-small cell lung cancer
NSG	nod-SCID gamma
open-label	A study in which there are no restrictions on knowledge of treatment allocation, therefore the investigator and the study participants are aware of the drug therapy received during the study.
ORR	objective response rate: the percentage of patients who achieve a best overall response (BOR) of CR or PR
OS	overall survival
PD	progressive disease
PD-1	programmed death 1
PD-L1	programmed death ligand 1

PFS	progression-free survival: the time from randomization until the first radiographic documentation of progression or death from any cause in the absence in progressive disease.
PK	pharmacokinetic
PR	partial response
PR3	proteinase-3
RECIST	Response Evaluation Criteria in Solid Tumors
reporting database	A point-in-time copy of the collection database. The final reporting database is used to produce the analyses and output reports for interim or final analyses of data.
Re-screen	to screen a patient who was previously declared a screen failure for the same study
RP2D	recommended Phase 2 dose
SAC	safety assessment committee
SAE	serious adverse event
SAP	Statistical Analysis Plan
screen	The act of determining if an individual meets minimum requirements to become part of a pool of potential candidates for participation in a clinical study.
Screen failure	A patient who does not meet one or more criteria required for participation in a study
SEC	staphylococcal enterotoxin B
sPD-L1	soluble programmed death ligand 1
SOC	system organ class
SUSAR	suspected unexpected serious adverse reactions
TBL	total bilirubin
TE	target engagement
TEAE	Treatment-emergent adverse event: an untoward medical occurrence that emerges during a defined treatment period, having been absent pretreatment, or worsens relative to the pretreatment state, and does not necessarily have to have a causal relationship with this treatment.
TMDD	Target Mediated Drug Disposition
TTR	Time-to-response

**Vd** volume of distribution

**WOCBP** Women of childbearing potential; females who have attained menarche and are not menopausal or surgically sterile.

---

